peripheral NK cells as well as increased activation and expression of the activating receptor, NKG2D. In addition, NK cells express PD-1 and therefore, can potentially be inhibited by its ligands suggesting treatment with PD-1 inhibitors could lead to subsequent activation of not only cytotoxic T cells but also NK cells. Therefore, combining metformin and PD-1 inhibition may enhance NK cell function and tumor cytotoxic response leading to improved survival outcomes. In fact, Scharping et al. showed that combining PD-1 blockade and metformin did enhance tumor growth inhibition in a melanoma mouse model which was thought to be due to a metformin related decrease in hypoxia allowing for immune cell infiltration. In this study, we will combine metformin and pembrolizumab in a phase II clinical trial in order to test clinical overall response in recurrent and/or metastatic HNSCC patients as well as determine the importance of NK cell infiltration, activation and possible mechanism in which the combination therapy exerts this effect.

Pembrolizumab and metformin have documented safety in several previous clinical trials and retrospective studies. A retrospective study comparing metastatic melanoma patients receiving PD-1 inhibitors versus those that were on the combination with metformin not only showed a trend towards improved clinical response, but also similar safety profiles with 60.6% vs. 59% immune related side effects respectively. A phase IB study in NSCLC also demonstrated early efficacy signals for the combination and similar safety profiles between pembrolizumab alone and combination. However, it is important to note that patients on these studies received metformin at doses of 500-1000mg daily. Given documented safety of the combination but not at the higher dose of metformin of 2000mg daily, we therefore feel it is reasonable to proceed with a phase II study with safety lead-in to determine dose limiting toxicity (DLTs) in this group of patients.

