## 7.7 Definition of Dose-Limiting Toxicity

### 7.7.1 Lead-in Safety Analysis

The first nine patients will be enrolled as the lead-in population. Safety analysis will be performed with this population and will be analyzed on a rolling basis. Monthly review with all active sites will be held to determine if any of these first 9 patients have experienced a dose limiting toxicity, DLT, (described below) to evaluate the safety of the combination. Safety analysis will be considered complete after the ninth patient has completed 28 days of combination treatment. Patients will continue to be enrolled past the initial safety cohort, but if at any time, safety analysis reveals >3 out of the 9 patients in the safety cohort have developed a DLT, then no further patients may be enrolled due to excess toxicity with this combination.

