### 7.7.2 Dose Limiting Toxicity

Dose limiting toxicity (DLT) is defined as the appearance of side effects during treatment that are attributed to treatment and severe enough to prevent continuation of treatment or grade 3 or 4 non-hematologic toxicities other than alopecia, nausea or vomiting and that in the case of pembrolizumab, do not resolve with steroids after four weeks. If more than three of nine patients develop a DLT, then combination will be considered unsafe and the study will not proceed. Patients are assessed for DLTs during the lead-in period as well as for the first 28 days of combination treatment.

Management and dose modifications associated with the above adverse events are outlined in Section 8.

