### 10.3 Early Stopping Rules:

In order to verify safety of the combination of metformin and pembrolizumab, an early stopping rule will be used if 3 out of 9 (33%) of the safety lead-in develop DLTs (see definition above). The lead-in will be on a rolling basis but if three patients develop DLTs, the study will be stopped so that safety may be investigated by the DSMB. If DLTs are confirmed, the study will be closed to enrollment due to safety concerns.

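### The DLT stopping rule counts only the nine lead-in patients, so DLTs in patients 10 to 25 reach no prespecified numeric trigger in the protocol

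*Combined protocol and SAP*

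**What the plan says.** The toxicity rule appears three times, always with nine patients as the denominator.

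- Section 7.7.1 bars further enrolment "if at any time, safety analysis reveals >3 out of the 9 patients in the safety cohort have developed a DLT". Its monthly review concerns those nine patients. It adds: "Safety analysis will be considered complete after the ninth patient has completed 28 days of combination treatment". It also says: "Patients will continue to be enrolled past the initial safety cohort".
- Section 7.7.2: "If more than three of nine patients develop a DLT, then combination will be considered unsafe and the study will not proceed". Its DLT window is the lead-in period plus the first 28 days of combination, and this sentence is not restricted to the first nine patients.
- Section 10.3: "an early stopping rule will be used if 3 out of 9 (33%) of the safety lead-in develop DLTs". On three DLTs, "the study will be stopped so that safety may be investigated by the DSMB", and confirmed DLTs close enrolment.

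Section 10.2 sets enrolment at 25. Section 3.3 explains the lead-in: "patients on these studies received metformin at doses of 500-1000mg daily", and "Given documented safety of the combination but not at the higher dose of metformin of 2000mg daily". Section 7.4.1 makes 2000 mg the target dose for every patient.

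Other oversight has no patient limit: dose rules (section 8), 24-hour SAE reports (11.3), ongoing review by the principal investigator (14.1), termination by that investigator (7.9), and regular review by an advisory DSMB that sees adverse event frequency and severity (14.3.1). None of these states a numeric criterion for stopping the study.

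**The concern.** The protocol judged that discretion alone was not enough for the first nine patients and gave them a limit of about one-third. It does not say why that limit lapses at patient 10, when the dose and combination are unchanged. Nine patients are a weak screen: a regimen with a true DLT rate above one-third can easily pass. If it does, the DLTs that would reveal the problem arise in the 16 patients whom the rule ignores. The investigator and the DSMB then see the data without a limit stated in the protocol.

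**Working it through.** **The plan's own figure.** Section 10.3: 3/9 = 33%, which reproduces. The protocol gives no operating characteristics for the rule.

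**Patients outside the rule.** 25 − 9 = 16, and 16/25 = 64%.

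**Inputs.** Lead-in of 9 (7.7.1); total of 25 (10.2); lead-in trigger of 4 or more DLTs (7.7.1, 7.7.2) or 3 or more (10.3). The true DLT rate p is not in the documents, so 10% to 40% is assumed. Patients are treated as independent.

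**Lead-in alone.** P(stop) = 1 − Σ C(9,x) pˣ(1−p)⁹⁻ˣ, summed over x = 0 to 3 (more than 3 of 9) or x = 0 to 2 (3 of 9). At p = 0.40 the terms for x = 0 to 3 are 0.010 + 0.060 + 0.161 + 0.251 = 0.483, so P(stop) = 0.517. For x = 0 to 2 the sum is 0.232, so P(stop) = 0.768.

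**Limit carried forward.** Let n be the number of patients with known DLT status. Pause at n = 10 to 25 if DLTs exceed n/3 (paired with more than 3 of 9) or reach n/3 (paired with 3 of 9). Among trials that have not crossed, the distribution of the DLT count is updated one patient at a time: fₙ(x) = (1−p)·fₙ₋₁(x) + p·fₙ₋₁(x−1). The mass at or above the boundary is removed as a crossing.

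Overall chance of a stop or pause, lead-in only → extended:

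| Assumed DLT rate | More than 3 of 9, then >n/3 | 3 of 9, then ≥n/3 |
|---|---|---|
| 10% | 0.8% → 2.2% | 5.3% → 6.1% |
| 15% | 3.4% → 8.9% | 14.1% → 17.2% |
| 20% | 8.6% → 21.6% | 26.2% → 33.5% |
| 25% | 16.6% → 39.3% | 39.9% → 52.1% |
| 30% | 27.0% → 58.4% | 53.7% → 69.4% |
| 40% | 51.7% → 87.2% | 76.8% → 91.8% |

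**Delay before a pause takes effect.** Section 10.2 expects 25 patients in 18 to 24 months, or 1.0 to 1.4 a month. The DLT window is 14 + 28 = 42 days (arm 1) or 21 + 28 = 49 days (arm 2), in which 1.4 to 2.2 more patients enter. A one-month wait for review takes this to as many as 3.6. A lag of 1 to 4 patients is used.

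**DLTs averted per trial started, upper bound.** p × Σ P(first crossing at n) × max(0, 25 − n − lag), assuming every pause becomes closure and nobody would otherwise act:

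- 20%: 0.2–0.3 (more than 3 of 9) or 0.1 (3 of 9)
- 25%: 0.4–0.6 or 0.2–0.3
- 40%: 1.1–1.5 or 0.4–0.5

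**A stricter boundary.** Pause only when the posterior probability that the rate exceeds one-third is above 0.90 (uniform prior: 6 DLTs at n = 10–11, rising to 12 at n = 25). At 40% the overall chance moves only from 51.7% to 61.0%, or from 76.8% to 79.0%. DLTs averted are at most 0.2.

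**The case against.** A rule confined to a safety lead-in is a legitimate design, and it is the one section 3.3 announces. Later patients remain under DSMB, SAE and investigator review. A 40% DLT rate has no support in the documents. Section 3.2.1 gives 6.3% grade 3 or higher immune-related events on pembrolizumab, and section 3.3 reports similar safety with lower-dose metformin. The gastrointestinal discontinuations in section 3.2.2 came mostly at 3000 mg, with some at 2550 mg. Here the dose is 2000 mg extended release, and section 8.1 allows reductions. A repeated check of the raw proportion against one-third is an eager boundary: at a true 30%, inside the limit, the chance of a stop or pause goes from 27.0% to 58.4%, or from 53.7% to 69.4%.

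Much of this stands. It makes the point optional, makes the averted counts upper bounds, and shows that the gain depends on the boundary. It does not supply a trigger for patients 10 to 25.

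Two stronger inferences fail. A reader might conclude that later patients are unmonitored, or that up to 3 + 16 = 19 of 25 could have a DLT with nothing done. The count is true of the rule but not of the trial, because the other safeguards continue. Nor can one say that no limit exists anywhere: no DSMB charter is among the documents.

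In the other direction, the clause in section 10.3 about three patients developing DLTs might be read as covering everyone. It sits in a sentence about the rolling lead-in, directly after the 3 of 9 rule, so it does not. Rolling review does mean that a late lead-in DLT can stop accrual after patient 10 has entered.

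**Conclusion.** The gap is real and worth closing, as a low-cost improvement. In the protocol, DLTs in 16 of 25 patients count toward no prespecified numeric trigger, at a metformin dose whose safety in combination the protocol itself calls undocumented. The benefit is material only if the true rate is well above the evidence cited for low toxicity and if more than 3 of 9 governs. At 10% to 15% the extension adds 0.8 to 5.5 percentage points to the chance of a stop or pause and averts little. Every rate is an assumption. The text finding does not depend on them.

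**What to change.** 1. Settle the lead-in threshold: section 10.3 says 3 of 9, while sections 7.7.1 and 7.7.2 say more than 3 of 9.
2. Amend 7.7.1 and 10.3 so that the existing monthly review counts DLTs in every patient, from the first dose of metformin or pembrolizumab through 28 days of combination. Include patients who stop during the lead-in period. Counting only those who start the combination would miss DLTs that prevent it, and section 13.1.1 already makes patients evaluable for toxicity from first treatment.
3. Pause enrolment for DSMB review when the limit is crossed after patient 9.
   - If more than 3 of 9 governs (>n/3): 4 DLTs at n = 10–11, 5 at 12–14, 6 at 15–17, 7 at 18–20, 8 at 21–23, 9 at 24–25.
   - If 3 of 9 governs (≥n/3): 4 at 10–12, 5 at 13–15, 6 at 16–18, 7 at 19–21, 8 at 22–24, 9 at 25.
4. State in 10.3 that its closure of enrolment on confirmed DLTs does not apply automatically to these later crossings.
5. Print the operating characteristics beside the rule. The statistician may choose a stricter boundary, which pauses less and gains less.

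The cost is a few sentences and one boundary line, using the review, data and DSMB already in place. The downside is unneeded pauses: the >n/3 version can pause at 4 of 10, one patient after 3 of 9 was acceptable. If a pause leads to closure, the trial may fall short of the 19 evaluable patients that the 6/19 criterion in section 10.2 needs.

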### 7.7.2 Dose Limiting Toxicity

Dose limiting toxicity (DLT) is defined as the appearance of side effects during treatment that are attributed to treatment and severe enough to prevent continuation of treatment or grade 3 or 4 non-hematologic toxicities other than alopecia, nausea or vomiting and that in the case of pembrolizumab, do not resolve with steroids after four weeks. If more than three of nine patients develop a DLT, then combination will be considered unsafe and the study will not proceed. Patients are assessed for DLTs during the lead-in period as well as for the first 28 days of combination treatment.

Management and dose modifications associated with the above adverse events are outlined in Section 8.

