## DOSING DELAYS/DOSE MODIFICATIONS

### 8.1 Metformin ER

Acceptable Dose Reductions for Metformin ER	
Dose Reduction Level	Dose Reduction
1	1000mg
2	500mg

Diarrhea	Management/Next Dose for Metformin ER
≤ Grade 2	No change in dose- can use loperamide to control
Grade 3**	Hold until ≤ Grade 2. Resume at same dose level. Decrease dose to 1000mg daily. Second occurrence can decrease to 500mg daily. Third occurrence, discontinue permanently.
Grade 4	Off protocol therapy
*Patients requiring a delay of >4 weeks should go off protocol therapy.	
**Ensure diarrhea is not due to pembrolizumab (see criteria below).	

Diarrhea	Management/Next Dose for Metformin ER

Recommended management: Loperamide antidiarrheal therapy  Loperamide dosage schedule: 4 mg at first onset, followed by 2 mg with each loose motion until diarrhea-free for 12 hours (maximum dosage: 16 mg/24 hours)  Adjunct anti-diarrheal therapy is permitted and should be recorded when used.
	

Nausea	Management/Next Dose for Metformin ER
≤ Grade 1	No change in dose
Grade 2	Hold until ≤ Grade 1. Resume at same dose level.
Grade 3	Hold* until < Grade 2. Resume at one dose level lower, if indicated.**
Grade 4	Off protocol therapy
*Patients requiring a delay of >4 weeks should go off protocol therapy.	
**Patients requiring > two dose reductions should go off protocol therapy.	
Recommended management: antiemetics.	

Vomiting	Management/Next Dose for Metformin ER
≤ Grade 1	No change in dose
Grade 2	Hold until ≤ Grade 1. Resume at same dose level.
Grade 3	Hold* until < Grade 2. Resume at one dose level lower, if indicated.**
Grade 4	Off protocol therapy
*Patients requiring a delay of >4 weeks should go off protocol therapy.	
**Patients requiring > two dose reductions should go off protocol therapy.	
Recommended management: antiemetics.	

Hypoglycemia	Management/Next Dose for Metformin ER
≤ Grade 1	No change in dose
Grade 2	Hold until ≤ Grade 1. Resume at same dose level.
Grade 3	Hold* until < Grade 2. Resume at one dose level lower, if indicated.**
Grade 4	Off protocol therapy
*Patients requiring a delay of >4 weeks should go off protocol therapy.	
**Patients requiring > two dose reductions should go off protocol therapy.	
Recommended management: antiemetics.	

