#### 8.2.4 Dose Discontinuation of Pembrolizumab

Treatment should be permanently discontinued for the following:

- Any Grade 2 drug-related uveitis or eye pain or blurred vision that does not respond to topical therapy and does not improve to Grade 1 severity within the re-treatment period OR requires systemic treatment.
- Any Grade 3 non-skin, drug-related adverse event lasting > 7 days, with the following exceptions for drug-related laboratory abnormalities, uveitis, pneumonitis, bronchospasm, neurologic toxicity, hypersensitivity reactions, and infusion reactions:
  - Grade 3 drug-related uveitis, pneumonitis, bronchospasm, neurologic toxicity, hypersensitivity reaction, or infusion reaction of any duration requires discontinuation.
  - Grade 3 drug-related laboratory abnormalities do not require treatment discontinuation except:
    - Grade 3 drug-related thrombocytopenia > 7 days or associated with bleeding requires discontinuation
    - Any drug-related liver function test (LFT) abnormality that meets the following criteria require discontinuation:
      - AST or ALT > 8 x ULN
      - Total bilirubin > 5 x ULN
      - Concurrent AST or ALT > 3 x ULN and total bilirubin > 2 x ULN
- Any Grade 4 drug-related adverse event or laboratory abnormality, except for the following events which do not require discontinuation:
  - Isolated Grade 4 amylase or lipase abnormalities that are not associated with symptoms or clinical manifestations of pancreatitis and decrease to < Grade 4 within 1 week of onset.
  - Isolated Grade 4 electrolyte imbalances/abnormalities that are not associated with clinical sequelae and are corrected with supplementation/appropriate management within 72 hours of their onset.
- Any dosing delay lasting > 8 weeks with the following exceptions:
  - Dosing delays to allow for prolonged steroid tapers to manage drug-related adverse events are allowed. Prior to re-initiating treatment in a subject with a dosing delay lasting > 8 weeks, the PI must be consulted. Tumor assessments should continue as per protocol even if dosing is delayed.
  - Dosing delays > 8 weeks that occur for non-drug-related reasons may be allowed if approved by the PI. Prior to re-initiating treatment in a subject with a dosing delay lasting > 8 weeks, the PI must be consulted. Tumor assessments should continue as per protocol even if dosing is delayed.

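### The four-week steroid clause in the DLT definition cannot be completed in the DLT window for pembrolizumab events that start during combination treatment, and its scope is unclear

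*Combined protocol and SAP*

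**What the plan says.** Section 7.7.2 defines a DLT through two limbs joined by an or. The first (the stopping limb) covers attributed side effects that prevent treatment from continuing. The second (the grade limb) covers Grade 3-4 non-hematologic toxicities with three named exclusions. The join reads "severe enough to prevent continuation of treatment or grade 3 or 4 non-hematologic toxicities". The grade limb, with its closing condition for one drug, runs "grade 3 or 4 non-hematologic toxicities other than alopecia, nausea or vomiting and that in the case of pembrolizumab, do not resolve with steroids after", and the period named there is four weeks.

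The window is in the same section: "Patients are assessed for DLTs during the lead-in period as well as for the first 28 days of combination treatment". Section 7.7.1 sets the cohort ("The first nine patients will be enrolled as the lead-in population") and the closing point: "Safety analysis will be considered complete after the ninth patient has completed 28 days of combination treatment". It provides for rolling assessment with monthly review and lets enrolment continue meanwhile. Neither section says how an event still unresolved at closure is counted.

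Section 8.2.4 lists events that require permanent discontinuation of pembrolizumab. They include "Any Grade 3 non-skin, drug-related adverse event lasting > 7 days" (with exceptions), certain named Grade 3 events such as pneumonitis whatever their duration, and most Grade 4 events. In section 8.1, the nausea and vomiting tables assign Grade 4 to "Off protocol therapy", although both symptoms are excluded by name from the grade limb.

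The stopping threshold is more than 3 of 9 in sections 7.7.1 and 7.7.2, but 3 of 9 (33%) in section 10.3.

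**The concern.** The lead-in exists because section 3.3 regards the combination as documented for safety, but not at this metformin dose. The DLT count drives the plan's only numeric safety stop, so each event needs one classification, available when the count is read.

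Two features prevent that. First, a test that takes four weeks is attached to a window that ends four weeks after combination treatment begins. Second, the four-week condition can be attached to the grade limb alone or to both limbs. Two sites following the same text could classify the same permanently discontinued patient differently. With nine patients and a threshold of three or four, one patient's classification can decide whether the study stops.

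**Working it through.** **Inputs.** Four-week clause and window: section 7.7.2. Closing point and cohort of nine: section 7.7.1. First pembrolizumab: Day 1 in Arm 1 and Day -21 in Arm 2 (study calendar, section 12). Thresholds: sections 7.7.1, 7.7.2 and 10.3. I take combination treatment to start on Cycle 1 Day 1, because the calendar places Days -21 to -7 under lead-in. I start the steroid clock on the day of onset, the earliest it could start and so the case most favourable to the plan.

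**The plan's own figure.** 3/9 = 33.3%, so the 33% in section 10.3 reproduces. The plan gives no target DLT rate or operating characteristics for the rule.

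**Timing.** An event with onset on day d completes the test 28 days later.
- Arm 1: d runs from Day 1 to Day 28, so the test ends on Day 29 at the earliest. Onset days that fit: 0 of 28.
- Arm 2: exposed days are Day -21 to Day -1 (21 days, no Day 0) plus Days 1 to 28, so 21 + 28 = 49. Onset on Day -1 completes on Day 28; onset on Day 1 completes on Day 29. Onset days that fit: 21 of 49 = 43%, all before Day 1.
- If the window closes after 28 elapsed days instead, the counts are 1 of 29 and 22 of 50.
- With 4 of the nine patients in Arm 2: 4×21 / (4×49 + 5×28) = 84/336 = 25%. With 5: 5×21 / (5×49 + 4×28) = 105/357 = 29%. The allocation ratio is not stated, so this split is an assumption.

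For onsets during combination, then, the clause can return only two answers inside the window: not a DLT (resolved early) or pending. It essentially cannot return DLT.

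**Scope of the clause.** Take a Grade 3 pneumonitis attributed to pembrolizumab that resolves on steroids in week 3. Section 8.2.4 requires permanent discontinuation.
- Clause on the grade limb only: the stopping limb is met, so it is a DLT.
- Clause on both limbs: it resolved within four weeks, so it is not a DLT.

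The grammar permits both, because the final relative clause parallels the one that opens the definition and governs both limbs.

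**What is left on the narrower reading.** A Grade 3 non-skin event that fails four weeks of steroids has long passed the 7-day point in section 8.2.4, so the stopping limb already counts it. Grade 4 nausea or vomiting that ends protocol therapy also counts there. Those left waiting on the four-week clause are mainly persistent Grade 3 skin events and laboratory abnormalities exempted in section 8.2.4.

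**Which patients are exposed.** Section 10.2 plans 25 patients over 18-24 months. With even accrual (an assumption), entries are about 548/25 = 22 to 730/25 = 29 days apart. Patient 7 enters two intervals, 44 to 58 days, before patient 9, leaving more than four weeks before closure. Patient 8 has about 22 to 29 days. If events may be classified after a patient's own Day 28, mainly patients 8 and 9 are exposed. Section 7.7.2 does not say that they may.

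**Threshold.** Exact binomial, n = 9, at assumed DLT rates of 20/30/40/50%: the chance of at least 4 is 8.6/27.0/51.7/74.6%, and of at least 3 is 26.2/53.7/76.8/91.0%. The rates are hypothetical; the comparison shows only how much one patient's classification can matter.

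**The case against.** The strongest reply is that failing one limb of an or does not undo meeting the other. Read that way, there is no contradiction with section 8.2.4 or the metformin tables: serious immune events that force discontinuation, and Grade 4 nausea or vomiting, are DLTs by the stopping limb. Section 7.7.2 also speaks of side effects appearing during treatment, which suggests an onset window. Rolling review to the ninth patient gives most earlier events time to mature. Pending events are not invisible either, since serious events are reported within 24 hours (section 11.3) and the DSMB sees adverse event frequency and severity (section 14.3.1).

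Most of this stands, and it limits the point. It does not remove it: the text does not choose that reading of the clause, does not state that the window is for onset, and has no rule for events pending at closure. Reporting an event is not the same as counting it toward the stopping rule.

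A reader might infer that the definition cannot be applied at all, or flatly conflicts with section 8. The documents do not support that. The window includes the lead-in, Arm 2 lead-in events can be classified, and the clause does not touch metformin events.

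A reader might also infer a collapse in the chance of stopping. Purely as a hypothetical, take a true DLT rate of 40%. Losing half the DLTs in all nine patients would cut the chance of at least 3 from 77% to 26%. Losing half in the ninth patient only would give 0.685 + 0.209 × 0.2 = 73% (eight patients at 40%: 0.685 for three or more, 0.209 for exactly two). The documents give neither the rate nor the share lost, so neither result is a finding.

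**Conclusion.** The concern holds in limited form. As written, the four-week test essentially cannot finish in the stated window for pembrolizumab events starting during combination treatment, and events pending at closure have no classification. This rests on the written window and on Cycle 1 Day 1 as the start of combination treatment.

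The consequence depends on an unstated choice. If the clause qualifies both limbs, events that require permanent discontinuation drop out of the count when they resolve on steroids within four weeks. If it qualifies the grade limb only, the gap is mainly events that do not require discontinuation, mainly in the last one or two lead-in patients under even accrual. The number of DLTs missed cannot be derived from the documents. I take no view on which clinical reading is right; the passages must be reconciled before the count is relied on.

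**What to change.** Amend the wording without changing care:

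- (a) Define the lead-in plus the first 28 combination days as the window for onset, and declare the lead-in complete only when every event with onset in that window has been classified.
- (b) List events awaiting the four-week outcome as pending at the monthly review and in the DSMB report.
- (c) State which limb the four-week clause qualifies, and reconcile sections 7.7.1, 7.7.2, 8.1, 8.2.4 and 10.3, including more than 3 of 9 against 3 of 9, so that each event has one classification and the count one threshold.

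The documents do not say whether the lead-in has closed. If it has, apply the clarified definition to the nine patients' recorded events and report the result to the DSMB.

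The cost is an amendment. Completion may be declared up to about four weeks later if an event is pending, while enrolment continues as section 7.7.1 already allows.
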